8.2.9 Anticipated adverse events

Injection related AEs such as bruising, erythema, itching, swelling, pain and tenderness are anticipated. Information regarding anticipated AEs for Restylane Volyme and Restylane Lyft Lidocaine are included in the IFUs (co-packed with product).

8.3 Device deficiencies

8.3.1 Definition of a device deficiency

A device deficiency is defined as an inadequacy of a medical device with respect to its identity, quality, durability, reliability, safety⁴, or performance.

Note: Device deficiencies include malfunctions, use errors, and inadequate labelling.

8.3.2 Recording instructions

When a device deficiency is discovered, Part A of the clinical study complaint form shall be completed by the Investigator. The type of complaint shall be described and injury to the subject or user or unintended exposure to study product shall be reported as applicable. If an injury has occurred, an AE or an SAE form shall be completed as applicable (refer to Section 8.2.4 and 8.2.5). If no SAE was experienced as a result of the device deficiency the Investigator shall assess whether or not the device deficiency could have led to an SAE if:

- Suitable action had not been taken,
- Intervention had not been made or,
- Circumstances had been less fortunate

In Part B of the clinical study complaint form the Sponsor will make the same assessment.

8.3.3 Reporting of device deficiencies

E-mail for device deficiencies reporting:

Fax number for device deficiencies reporting:

Effective

⁴ Inadequacy of device safety refers to properties of the device which could have or have led to an AE.

A device deficiency that led to a SAE and any device deficiency that could have led to a SAE shall be reported to the Sponsor within 24 hours after the Investigator's awareness (for contact information, see Section 8.2.5).

If the Investigator or the Sponsor assesses that the device deficiency could have led to a SAE the Sponsor is responsible for reporting the device deficiency to RA and the PI is responsible for reporting it to the IEC.

The deficient study product shall be kept by the study site until the Sponsor has confirmed whether the product shall be returned to Sponsor for further study or if it can be destroyed at the study site.

9. Data Handling and Management

9.1 Data management

Data management based on GCP refers to the activities defined to achieve safe routines to enter clinical data information into a database, efficiently and avoiding errors. The data management routine includes procedures for database set-up and management, data entry and verification, data validation, and documentation of the performed activities including information of discrepancies in the process. The data management process will be described in detail in the data management plan (DMP).

The database, the data entry screens and program will be designed in accordance with the CSP and the CRF template. Data validation will be performed by computerized logical checks and manual review. Drugs and events will be coded in accordance with World Health Organization (WHO) Drug and medical dictionary for regulatory activities (MedDRA) dictionaries as specified in the DMP. Safety data (SAE and if applicable AE of special interest) in the clinical database will be reconciled against the data in the safety database.

When all efforts have been made to ensure that the data recorded in the eCRFs and entered in the database is as correct and complete as possible, the clinical database will be locked. Study data will be transferred to SAS datasets, which thereafter will be write-protected. Statistical analyses will be generated in SAS using data from the locked datasets.

9.2 Electronic case report forms

An electronic data capture application, compliant with regulatory requirements for software validation will be used to collect, modify, maintain, archive, retrieve, and transmit study data. An eCRF is required and shall be completed electronically for each screened subject (screening visit) and included subjects (subsequent visits).

The eCRF includes password protection and internal quality checks, such as automatic range checks, to identify data that appear inconsistent, incomplete, or inaccurate. Study data shall be entered directly from the source documents, which are to be defined at each site before inclusion of the first subject.

Authorized study site personnel designated by the PI shall complete data collection. Appropriate training and security measures shall be completed with all authorized investigation site personnel prior to the study being initiated and any data being entered into the system for any subject.

The study data is the sole property of the Sponsor and shall not be made available in any form to third parties, except for authorized representatives of appropriate RA, without written permission from the Sponsor. At the end of the study, electronic data are kept at the Sponsor and a copy (provided by the vendor) at the study site as part of the Investigator file.

Any delegation of collection of data shall be specified and recorded.

9.2.1 Data entry

All data shall be entered in English. The eCRFs should always reflect the latest observations on the subjects participating in the study. Therefore, the eCRFs shall be completed as soon as possible during or after the subject's visit. The subject's identity must always remain confidential, i.e. the name and address of the subjects must not be registered in the eCRFs or in the database. The Investigator must verify that all data entries in the eCRFs are accurate and correct. If some assessments are not done, or if certain information is not available, not applicable or unknown, the Investigator shall indicate this in the eCRF. The Investigator shall electronically sign off the study data. By signing, the Investigator takes responsibility for the accuracy, completeness, and legibility of the data reported to the Sponsor in the eCRF.

9.2.2 The query process

The monitor shall review the eCRFs and evaluate them for completeness and consistency. Each eCRF shall be compared with the respective source documents to ensure that there are no discrepancies between critical data. All entries, corrections, and alterations shall be made by the PI or his/her authorized designee. The monitor cannot enter data in the eCRFs. Once study data have been submitted to the central server via the eCRF, corrections to the data fields will be audit trailed, meaning that the reason for change, the name of the person who made the change, together with time and date will be logged. Roles and rights of the site personnel responsible for entering study data into the eCRF shall be determined in advance. If discrepant data is detected during review of the data, either by the Sponsor or by its representatives, the responsible data manager or monitor shall raise a query in the electronic data capture application. The query shall state the question or data to be changed and shall be resolved in the system by the PI or his/her authorized designee. The appropriate study site personnel shall answer the queries in the eCRF. This will be audit trailed by the electronic data capture application meaning that the name of study site personnel, time, and date is logged.

9.2.3 User identification

Electronic CRF records will be automatically appended with the identification of the creator, by means of their unique UserID. Specified records shall be electronically signed by the Investigator to document his/her review of the data and acknowledgement that the data are accurate. This will be facilitated by means of the Investigator's unique UserID and password; date and time stamps will be added automatically at time of electronic signature. If an entry in an eCRF requires change, the correction shall be made in accordance with the relevant software procedures.

9.2.4 Audit trail

All changes will be fully recorded in a protected audit trail and a reason for the change shall be stated. Once all data have been entered, verified, and validated, the database will be locked.

9.3 Source documents

The eCRF is essentially considered a data entry form and does not constitute the original (or source) medical records unless otherwise specified. Source documents are all documents used by the Investigator or hospital that relate to the subject's medical history, that verifies the existence of the subject, the inclusion and exclusion criteria, and all records covering the subject's participation in the study. They include laboratory notes, memoranda, material dispensing records, subject files, etc.

Title

The PI is responsible for maintaining adequate and accurate source documents. Source data should be attributable, legible, contemporaneous, original, accurate, and complete. Changes to source data should be traceable, should not obscure the original entry and should be explained if necessary.

These shall be made available for inspection by the monitor at each monitoring visit. The Investigator must submit a completed eCRF for each subject for whom signed informed consent has been collected. All supportive documentation submitted with the eCRF, such as laboratory or hospital records, shall be clearly identified with the clinical trial number (CTN) and subject number. Any personal information, including name, shall be removed or rendered illegible to preserve individual confidentiality.

9.4 Record keeping and access to source data

The PI/Institution shall permit study-related monitoring, audits, IEC review, and RA inspections and shall provide direct access to the source data/medical record including the identity of all participating subjects (sufficient information to link records, i.e. eCRF, medical records, original signed informed consent forms and detailed records of study product accountability). The records shall be retained by the PI as required by local legislation and international guidelines. Any transfer of responsibility for storage of the records shall be documented and the Sponsor shall be informed in writing.

The Sponsor shall verify that each subject has consented in writing to direct access to the original medical record/source data (by the use of written subject information and signed informed consent). The data recorded in the eCRFs will be checked for consistency with the source documents/medical record by the monitor during monitoring (source data verification; SDV). In order to be able to perform SDV, information about each subject's participation in the study has to be detailed in the medical record or other relevant source.

9.5 Document and data retention

All records pertaining to the conduct of the study, including signed eCRFs, informed consent forms, study product accountability records, source documents, and other study documentation must be retained for 15 years after study completion or longer if required by national legislation. Sponsor will inform the site(s) as to when these documents no longer needs to be retained. Measures shall be taken to prevent accidental or premature destruction of these documents (e.g. protection against damage and unauthorized access, preferably by storage in a fireproof cabinet).

It is the PI's responsibility to inform the Sponsor in writing if the Investigator file is moved or if the responsibility for the documents is transferred to someone else.

10. Statistical Methods

10.3 Demographics, baseline assessments, and subject characteristics

Demographic endpoints, baseline assessments, and subject characteristics will be presented based on the FAS, using descriptive statistics.

10.4 Efficacy analysis

40(45)

10.5 Safety analysis

The number of subjects with AEs related to study product or injection procedure as well as the number of events will be summarized by SOC, PT, and maximum intensity.

10.6 Handling of missing data

Study data will be presented based on observed cases, i.e. no imputation of missing values will be performed.

10.7 Interim analysis

Not applicable as this is an open study.

10.8 Withdrawals and deviations

All withdrawn subjects will be listed individually, including at least subject number, date and reason for withdrawal, and last visit performed.

Subjects with CSP deviations will be listed individually, including subject number and observed deviation. Depending on the seriousness of the deviation, subject might be excluded from the PP population, which shall be documented prior to database lock.

Deviations from the statistical plan will be documented in the statistical report.

10.9 Sample size

Effective

11. Protection of personal data

All processing of personal data must be carried out in accordance with national legislation concerning the protection of personal data, including the Personal Information Protection and Electronic Documents Act (PIPEDA). The Institution and the PI are responsible for complying with

Title

all requirements pursuant to national legislation in the country in which the Institution and the PI are located. The Sponsor will ensure that all requirements are complied with for data processing.

The informed consent form shall contain information about what personal data to be collected in the study and that this will be kept confidential. The provided information shall be sufficient to enable all subjects to give their consent not only to the participation in the study, but also to the processing of personal data. Such information includes information regarding the purposes of the collecting, processing, data transfer to other countries. If a subject decides to terminate the study prematurely, data collected before withdrawal of consent will be used in the evaluation of the study, however no new data may be collected. Authorized representatives from the Sponsor, contract research organization (CRO) or a RA may visit the study site to perform audits/inspections, including SDV, i.e. comparing data in the subjects' medical records and the eCRF. Data and information shall be handled strictly confidential.

12. Quality Control and Quality Assurance

12.1 Quality control

On-site monitoring of the study will be arranged by the Sponsor according to GCP guidelines to verify that the rights and well-being of the subjects are protected, the reported data are accurate, complete, verifiable from source documents, and that the conduct of the study complies with the approved CSP, subsequent amendment(s), GCP and the applicable regulatory requirements.

Any CSP deviation shall be documented appropriately, verified, discussed, and collected by the monitor and appropriate actions will be taken. The PI is responsible for promptly reporting any deviations from the CSP that affects the rights, safety or well-being of the subject or the scientific integrity of the study, including those that occur under emergency circumstances, to the Sponsor as well as the IEC if required by national regulations. Deviations will be reviewed to determine the need to amend the CSP or to terminate the study.

12.2 Quality assurance

The study site may be subject to quality assurance (QA) audit by the Sponsor as well as inspection by appropriate RA. It is important that the PI and other relevant study site personnel are available during the monitoring visits, possible audits, and inspections, and that sufficient time is devoted to the monitoring process.

Each participating member of the study site team shall provide a curriculum vitae (CV) or equivalent that demonstrates their qualifications to conduct the study.

It is the responsibility of the PI to ensure that all personnel involved in the study are fully informed of all relevant aspects of the study, including detailed knowledge of and training in all procedures to be followed. All Investigators and other responsible persons shall be listed together with their function in the study on the signature and delegation log.

Effective

CALDERMA

13. Financing, Indemnification, and Insurance

This is a Galderma fully sponsored study. The CTA between sponsor and Investigational sites outlines the compensation and payment terms of the study. The CTA must be signed before the first subject is screened in the study. If there are differences between the CTA and the CSP regarding certain rights and obligations, the CTA is the prevailing document. Q-Med AB's obligations in this clinical study are covered by Galderma's global general liability program. An insurance certificate will be provided upon request. The Institution/PI is obligated to maintain insurance coverage for their obligations in the clinical study according to the CTA.

15. Suspension or Premature Termination

The Sponsor will suspend or terminate the study when so instructed by the IEC or RA, or if it is judged that the subjects are subjected to unreasonable risks, or for valid scientific or administrative reasons, or for business reasons.

The Sponsor may also decide to close a single study site due to unsatisfactory subject enrollment or non-compliance with the CSP, GCP, or applicable regulatory requirements.

⁵ Defining the role of authors and contributors, compiled by the International Committee of Medical Journal Editors (ICMJE) (http://www.icmje.org).

In the event of premature termination, Q-Med AB will provide information on the handling of currently enrolled subjects who have not completed the study.

16. References

1.0 PURPOSE

This SAP describes the methods to be used in the analysis of trial data from clinical protocol CTN 05DF2004 titled "A Study Comparing Hyaluronic Acid Effectiveness & Evaluating Cheek Results with Restylane" in order to answer the trial objective(s) and is based on v1.0 of the trial protocol, dated 03NOV2020.

Populations for analysis, data handling rules, statistical methods, and formats for data presentation are described within this document. The statistical analyses and summary tabulations described in this SAP will provide the basis for the results sections of the CSR for this trial. The SAP outlines any differences in data analysis methods relative to those planned in the trial protocol. Any changes to the data analysis methods after the SAP is finalized will be described in the CSR.

Effective

Version: 1.0

2.0 ACRONYMS

Below is the list of acronyms that will be used throughout this document.

Abbreviation	Definition
AE	Adverse Event
ATC-4	Anatomical Therapeutic Chemical 4th level
BMI	Body Mass Index
CSP	Clinical study protocol
CSR	Clinical Study Report
eCRF	Electronic Case Report Form
FST	Fitzpatrick Skin Type
[REDACTED]	[REDACTED]
IPR	Independent Photographic Reviewer
FAS	Full Analysis Set
MedDRA	Medical Dictionary for Regulatory Activities
PP	Per Protocol
PT	Preferred Term
SAP	Statistical Analysis Plan
SD	Standard Deviation
SOC	System Organ Class
SOP	Standard Operating Procedure
TC	Telephone Call
WHO	World Health Organization

3.0 OVERALL STUDY DESIGN AND OBJECTIVE

3.1 Trial Objectives

3.1.1 Primary Objective

To evaluate the aesthetic improvement (cheek appearance) with Restylane® Volyme and Restylane® Lyft Lidocaine compared to pre-treatment.

The primary endpoint:

- Improvement assessed by the Treating Investigator week 4 after last treatment, [REDACTED]

3.1.2 Secondary Objectives

Sponsor: Galderma

Protocol Number: CTN 05DF2004

Plan Version: 1.0

Effective

Version: 1.0

3.1.3 Safety Objective

To evaluate the safety of Restylane® Volyme and Restylane® Lyft Lidocaine by assessment of adverse events (AEs) by the Treating Investigator throughout the study period.

3.2 Trial Design and Trial Procedures

This is an 8-week, multi-center, phase IV, post-marketing study

Title
05DF2004 SAP

Doc id

Sponsor: Galderma

Protocol Number: CTN 05DF2004

Plan Version: 1.0

Approximately 60 female subjects will be treated at 3 sites in Canada.

[REDACTED]

[REDACTED]

Version: 1.0

[REDACTED]
[REDACTED]
[REDACTED]
[REDACTED]
[REDACTED]

05DF2004 SAP

Advanced Clinical

Doc 10

Sponsor: Galderma

Protocol Number: CTN 05DF2004

Plan Version: 1.0

Effective

Version: 1.0

3.3 Treatments and Assignment to Treatments

Approximately 60 subjects will be enrolled at 3 sites in Canada.

Template #: ST-T-002A, Ver.: 4.0

**Template #: ST-
CONFIDENTIAL**

EXCLUSIVE PROPERTY OF ADVANCED CLINICAL, LLC

Page 8 of 22

4.0 GENERAL STATISTICAL METHODS

4.1 Determination of Sample Size

The sample size of approximately 60 subjects [REDACTED] is not based on a statistical calculation. The selected number of subjects is regarded as sufficient for an evaluation of effectiveness and safety of the two products for cheek augmentation/volumization [REDACTED]

4.2 General Methods

All tables, listings, and figures will be programmed using SAS Version 9.4 or higher. Data collected in this study will be documented using summary tables and subject data listings created by using the SAS® system. Confidence intervals (CI) and p-values will be 2-sided and performed at a significance level of 5%, unless otherwise specified. Data for all subjects in the clinical database will be included in the data listings. Calculated (derived) variables will be listed as appropriate. Any changes from the SAP will be detailed in the clinical study report.

All efficacy, safety and baseline characteristics variables will be presented using descriptive statistics within each treatment group, and graphs as appropriate. Continuous variables will be summarized using descriptive statistics (number of observations, mean, standard deviation [SD], median, minimum, and maximum). Categorical variables will be presented in frequency tables with number and percentage of observations for each level. Missing counts for all variables will be presented for informational purposes only and will not be included in percentage calculations.

Study days will be calculated relative to the injection of study drug. Day 1 will be the day of study drug administration. Baseline will be the last assessment prior to the injection of study drug unless otherwise indicated. The Screening Visit 1 (Day -30 to Day 0) will be considered the visit prior to injection of study drug. Because the Screening visit and Baseline visit (Day 1) may be performed on the same day, the Screening visit can also be Day 1.

Adverse events, prior dermatological procedures or implant history events, medical history events, and concomitant treatments/procedures will be coded using MedDRA, Version 23.0. Prior/concomitant medications and procedural anesthetics will be coded using the World Health Organization (WHO) Drug Dictionary Global, 1 March 2020 or higher.

 GALDERMA Advanced Clinical	Title 05DF2004 SAP	Doc id [REDACTED]
--	------------------------------	----------------------

Sponsor: Galderma

Protocol Number: CTN 05DF2004

Plan Version: 1.0

In general, efficacy and safety analyses will be performed and summarized by treatment group, unless otherwise stated.

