4.5 Handling of Missing Data

Study data will be presented based on observed cases, i.e. no imputation of missing values will be performed.

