4.7 Multiple Comparisons/Multiplicity

No adjustments for multiple comparisons or multiplicity will be made. P-values obtained for any endpoint other than the primary will only be provided for ease of interpretation of the results.

	
Title 05DF2004 SAP Advanced Clinical
	
Doc id [REDACTED]

--	--	------------------------------

Sponsor: Galderma

Protocol Number: CTN 05DF2004

Plan Version: 1.0

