5.1 Full Analysis Set (FAS)

Includes all subjects who were injected in both cheeks. FAS is the primary population for all effectiveness analyses.

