7.0 EFFICACY ANALYSIS

7.1 Primary Efficacy

7.1.1 Primary Efficacy Endpoint

The primary efficacy endpoint is [REDACTED]
assessed by the Treating Investigator week 4 after last treatment compared to
pre-treatment.

Effective

Version: 1.0

Very much worse

Obvious worsening in appearance from the initial condition.

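### Does leaving unrated subjects out of the week-4 percentages make the primary result unsound?

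*SAP*

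**What the plan says.** SAP 4.2 sets the tabulation rules. For categorical data, "Categorical variables will be presented in frequency tables with number and percentage of observations for each level". On missing values, "Missing counts for all variables will be presented for informational purposes only and will not be included in percentage calculations". On grouping, "In general, efficacy and safety analyses will be performed and summarized by treatment group, unless otherwise stated".

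SAP 4.5 gives the missing-data rule: "Study data will be presented based on observed cases, i.e. no imputation of missing values will be performed". Protocol 10.6 says the same.

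SAP 5.1 defines the Full Analysis Set (FAS): "Includes all subjects who were injected in both cheeks. FAS is the primary population for all effectiveness analyses". No post-treatment rating is needed for membership.

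The legible part of the primary endpoint in SAP 3.1.1 is "Improvement assessed by the Treating Investigator week 4 after last treatment". SAP 7.1.1 leaves one level of the rating scale readable, described as "Obvious worsening in appearance from the initial condition". The rest of the endpoint definition and the bodies of SAP 7.1.2 and Protocol 10.4 are not visible in the public documents.

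Three other sections bear on the point. SAP 4.4 keeps out-of-window assessments and tabulates them at the visit recorded in the eCRF. SAP 6.1 summarises completion and discontinuation reasons on the FAS. Protocol 5.5 asks for a full assessment of subjects who leave early, where possible.

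**The concern.** The FAS is labelled as all subjects injected in both cheeks, yet a percentage calculated under SAP 4.2 covers only those who were rated. A table headed FAS could then report on fewer people than its heading suggests. If subjects who improved less were also less likely to return, the percentage improved would be too high.

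The study is open-label and has no reference product, about 60 subjects, and a sample size that SAP 4.1 says does not come from a statistical calculation. The week-4 rating carries the main effectiveness message, so a reader might expect a table on the full FAS denominator, fixed in advance, showing how far unrated subjects could move it.

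**Working it through.** **What the visible text fixes.** The counting rule for unrated subjects is already settled before the data are seen: SAP 4.2 leaves them out of the percentage and displays their number, and SAP 4.5 and Protocol 10.6 exclude imputation. These statements agree. An early-termination rating is also largely settled: SAP 4.4 tabulates by recorded visit, so on the visible text it is not a week-4 rating.

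**Inputs.** N = 60 is the planned total (SAP 3.2). The documents give no missing rate, response rate or visible split between products. The missing counts, the rate near 90% and any group of 30 are assumptions. The confidence interval method is not visible either; exact (Clopper-Pearson) two-sided 95% intervals are used here. There is no figure in the plan to reproduce.

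**Formulas.** With N in the FAS, m unrated and x rated improved:

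- observed-case percentage: x/(N − m)
- lower bound (missing counted as not improved): x/N
- upper bound (missing counted as improved): (x + m)/N
- range between bounds: m/N
- observed-case minus lower bound: [x/(N − m)] × (m/N)

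**Results for N = 60, about 90% improved among those rated.**

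| m | Observed-case (95% CI) | Lower bound | Upper bound | Observed minus lower |
|---|---|---|---|---|
| 1 | 53/59 = 89.8% (79.2–96.2) | 53/60 = 88.3% | 54/60 = 90.0% | 1.5 points |
| 2 | 52/58 = 89.7% (78.8–96.1) | 52/60 = 86.7% | 54/60 = 90.0% | 3.0 points |
| 3 | 51/57 = 89.5% (78.5–96.0) | 51/60 = 85.0% | 54/60 = 90.0% | 4.5 points |
| 6 | 49/54 = 90.7% (79.7–96.9) | 49/60 = 81.7% | 55/60 = 91.7% | 9.1 points |
| 9 | 46/51 = 90.2% (78.6–96.7) | 46/60 = 76.7% | 55/60 = 91.7% | 13.5 points |

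Up to six missing (10%), the worst case lies inside the observed-case interval. At nine missing (15%) it falls below the lower limit (76.7% against 78.6%). In an assumed product group of 30 with three missing, 24/27 = 88.9% (70.8–97.6) compares with bounds of 24/30 = 80.0% and 27/30 = 90.0%, again inside the interval.

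**Can a reader obtain the bounds without an extra table?** Yes. SAP 4.2 prints the number at each level and the number missing. Given 49 improved of 54 rated and 6 missing, the denominator is 54 + 6 = 60. The bounds are then 49/60 and (49 + 6)/60.

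**What would the extra table change?** The observed-case result would stay the main one. A row counting missing as not improved gives only the lower bound, although the direction of any bias is unknown: the observed percentage is too high if unrated subjects improved less often than rated ones, too low if they improved more often, and unaffected if equally often.

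**The case for a change.** The strongest argument for a full-FAS table is that it costs a few lines, gives the lower bound its own confidence interval, and could say explicitly how an early-termination rating is counted. The SAP also departs from strict non-imputation elsewhere: SAP 7.4 assumes the highest severity when an adverse event's severity is missing, and fills in missing start dates. A conservative rule for the primary endpoint would fit that practice. SAP 4.7 adds that "P-values obtained for any endpoint other than the primary will only be provided for ease of interpretation of the results", which implies a p-value may be attached to the primary endpoint.

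Some of this stands. The mechanism is real if the result is a percentage improved, and with nine or more of 60 missing the worst case would leave the observed-case interval. Such a table would be harmless and mildly useful.

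It does not amount to a fault. Conservative rules for adverse event tables do not make an observed-case rule for effectiveness wrong. A possible p-value does not help either, because the test and its hypothesis are not visible. Nor is any success threshold that a changed denominator could cross. The percentage form itself is inferred from one word and one scale level, and the blanked analysis sections may already hold a full-FAS analysis.

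**Conclusion.** The concern does not hold. The plan states one consistent, openly disclosed rule for unrated subjects and prints the counts needed to undo it. No visible statement, figure or decision rule is contradicted by it.

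The possible effect is m/N between the two extremes: 1.7 points per unrated subject at N = 60, or 3.3 points in an assumed group of 30. At about 90% observed, the drop to the worst case is 3.0 points with two missing and 9.1 points with six, all recoverable from the planned tables. These sizes rest on assumed missing and response rates and on the inferred percentage form of the endpoint. Heavy loss of week-4 ratings would call for caution in reading the result, and the displayed missing counts would reveal it.
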